#### ***B5. Study Entry***

Once a patient provides written consent, they are enrolled as a study participant. After a research coordinator obtains consent, s/he enters a participant's preferred phone number, contact method (text or phone message), and preferred contact times into the research account on the Epharmix/CareSignal Intervention Builder platform via the web portal [epx.wustl.edu](http://epx.wustl.edu). They also include the referral clinic name, clinic phone number, and clinic address that the treating ED staff instructs the patient to call for a follow-up appointment. It is possible to include more than one referral clinic if the ED staff provides a second option.

#### ***B6. Randomization Method and Blinding***

Once a participant is added to the Intervention Builder account, the integrated software independently randomizes participants to either the control or the intervention arm. The software s randomly allocates participants in a 1:1 ratio to intervention and control arms.

Even though participants are not informed if they were enrolled in the intervention or control arm, they are capable of inferring this information (if they did or did not receive a text or phone call).

Treating clinical staff are blinded to arm allocation. They complete treatment before a participant enrolls in the study.

The research team will be blinded to arm allocation whenever possible. EMR review to identify attended follow-up appointments and ED re-visits will be completed before intervention responses are reviewed and analysis commences.

#### ***B7. Follow-Up Communication***

There was not any follow-up communication in this research study.

#### ***B8. Clinical Workflow Precautions***

Following discharge from an emergency department (ED), it is standard of care that patients receive written instructions and counseling from ED staff (physicians, nurses and as-needed social workers). Discharged patients are not normally contacted by ED staff after leaving the ED. The intervention is considered an add-on to this standard of care by facilitating communication to the participant's designated provider for their follow-up appointment.

In the event that a discharged patient begins showing new signs or symptoms that required clinical evaluation before leaving the ED, the patient is required to start the standard clinical care process over again in compliance with ED guidelines and the Emergency Medical Treatment and Labor Act. Depending on the outcome of the subsequent evaluation, the patient may or may not meet research criteria, which is determined by the patient's final disposition.

If a participant's ED visit results in scheduling a follow-up appointment at the time of their discharge, such as for a specialist consultation or social worker visit, they are not included in the study.

### **B9. Participant Withdrawal**

If any participant wants to withdraw from the #201504079 study they may call the number listed at the top of the written consent form and ask the project lead or principal investigator to send a copy of a withdrawal letter to fill out, or they could follow instructions in the consent form to go to the Human Research Protection Office website and print off their own copy of a withdrawal letter. They would mail the letter to the address given at the top of the consent form [see Appendix 1. Written Consent Form].

The research coordinator reviews this process with the participant at the time of their written consent. Participant data collected up to the time of withdrawal will still be analyzed. If the participant was still receiving automated messages when the research team received a withdrawal letter, the project lead located the participant's information in the EPharmix/CareSignal Intervention Builder and discontinues the intervention from the research account.

## C. Study Procedure

### **C1. Intervention Treatment**

After providing written informed consent, participants in the intervention arm begin receiving text or voice messages to help them schedule a follow-up appointment with the referral provider per the pseudocode template attached [see Appendix 5. Pseudocode]. By default, participants receive automated messages starting one hour following discharge if it is normal business hours (Monday through Friday 0900 to 1700), or at 1000 the next business day if they are discharged outside of normal business hours. Automated messages are sent up to three days in a row or until the participant responded or the participant opted out, whichever occurs first. The participant is able to respond to all messages by either using alphanumeric (1-3) or binary answers (Yes or No). The primary goal of the intervention is to connect the participant directly to the referral provider's office to schedule an appointment. Once the participant hangs up with the office, the intervention asks if they were successful with scheduling an appointment.

If the participant fails to respond to the intervention, the intervention leaves a voicemail detailing instructions on how to reach the referral provider's office via a toll-free phone number. This toll-free number is the same number that showed up on the participant's cell phone or landline caller ID when the intervention reached out to them. If the participant calls the toll-free number, the intervention works as it normally would.

Once an appointment is made, the system sends reminders at 14 days, 7 days, 3 days, and 1 day before the appointment date. The day after the appointment, the intervention contacts the participant to see if they attended it. If the participant did attend, the intervention stops. If the participant did not attend and needs to reschedule, the intervention resets and starts over again.

Participants can voluntarily opt-out of receiving any further messages at any time if they text STOP or if they press \* on the keypad during an automated phone message.

Participants in the control arm do not receive any messages.

### **C2. Participant Education on Research vs Clinical Care**

At the time of written consent the research coordinator will advise participants that the messages they may receive are not coming from their treating physicians or clinical staff, but from an automated system that is separate from their medical care because it is only part of a research study. Participants

are advised that if they have any health concerns, the automated system would not be able to help them and they need to reach out to their doctor or the emergency room as they normally would. If the participant feels they are having a health concern related to the study, they are encouraged to call the phone number to the main study contact at the top of their consent form. If the research team is notified, they will follow reporting procedures for an adverse event [see Section F2. Reporting of Adverse Events].

### ***C3. Changes to Standard of Care***

No automated clinical judgements are included in this study. The purpose of utilizing the Epharmix/CareSignal Intervention Builder in this study was purely to facilitate follow-up visits to referral providers.

## **D. SMS and Phone Application**

### ***D1. Epharmix/CareSignal***

This study under umbrella IRB 201504079 uses the Epharmix/CareSignal Intervention Builder platform to develop an automated outreach that facilitates patient follow-up visits with referral providers and collects appointment follow-up rates. The platform utilizes two-way text messaging or automated phone calls to acquire data from participants, at intervals set by the principal investigator. The research team's unique account on the Epharmix/CareSignal Intervention Builder collected follow-up appointment data. Only one Epharmix/CareSignal employee, the Chief Developer, had access to the Intervention Builder platform in order to provide routine maintenance. This employee had updated HIPAA and CITI training. The Epharmix/CareSignal Intervention Builder was not a phone application; participants did not need to download or install anything on their phones in order to receive the research texts or phone messages. Participant phone responses were automatically stored on the Epharmix/CareSignal Intervention Builder site, [epx.wustl.edu](http://epx.wustl.edu), in the specific research account that is password protected. Epharmix/CareSignal, Inc does not have access to this password. In addition, the site is SSL-encrypted, ensuring password safety in transmission.

### ***D2. Regulatory Status***

The FDA has not made an assessment of risk with regard to this study, and as a communication tool we are not requesting to conduct this study under FDA NSR requirements. Epharmix/CareSignal Intervention Builder is not an implant and does not present a potential for serious risk, does not support or sustain human life, and is not of substantial importance in diagnosing, curing, mitigating, or treating disease, and does not have serious risk for health, safety, or welfare of a subject.

### ***D3. Method of Use of Epharmix/CareSignal Intervention Builder***

After enrollment, the research coordinator will initiate use of the research account's intervention that was built on the Epharmix/CareSignal Intervention Builder. The research account will send an initial text message or phone call as described in Section C1. Intervention Treatment. Since patients discharged from the ED do not have any further contact with ED providers, this intervention is not designed to sustain communication between the clinical provider and the participant. This intervention is instead fully automated to connect participants to a referral provider or service. It does not request health information from participants nor deliver any health information to them. The pseudocode responds to a participant's success in setting up a follow-up appointment and provides alternate choices if a follow-up appointment could not be made [see Appendix 5. Pseudocode].

Once the intervention is completed with the last enrolled participant, the project lead will request that the Epharmix/CareSignal Chief Developer aggregate and extract a raw data file (.csv) from the research account that the study manager encrypted so that the data is unviewable by the Chief Developer. The Chief Developer places this encrypted data file on an encrypted flash drive that is handed off to the project lead. The project lead uploads the encrypted file onto a secure database on box.wustl.edu.

#### **D4. Alert Management**

No alerts were used as a part of the intervention.

#### **E. Follow-up Visit Schedule**

No additional follow-up visits were required for this study. Participants followed up with their referral providers as they normally would.

#### **F. Data Collection and Analysis**

##### **F1. Outcome Assessments**

The outcomes of interest are:

- Primary: Participant follow-up attendance to a referral clinic or provider (compliant / non-compliant).
- Secondary:
  - Number of re-admissions to the ED (BJH or other) within 30 days and again within four months post-discharge.
- Tertiary:
  - Patient engagement levels with the intervention: number of successful attempts to reach participant, number of successful attempts to schedule a follow-up appointment, length of phone call to schedule an appointment, and number of successful follow-up appointments with a specialist provider versus a primary care provider.

To minimize bias, all clinical staff and research team members conducting patient chart reviews will be blinded to participant arm allocation [see Section B6. Randomization Method and Blinding]. We anticipate the study will have no impact on clinical workflow since the intervention will take place during a gap in clinical care when a participant is transferred between providers and we will only be completing patient chart assessments and data analysis to finalize the study.

##### **F2. Confidentiality and Security**

The Epharmix/CareSignal Intervention Builder has been evaluated by WU IT security before and approved for other studies [see Appendix 7. Security Clearance]. Participant responses to the intervention are stored on a HIPAA compliant WU server at epx.wustl.edu that has both encryption and penetration testing. Data was exported upon request after being de-identified in a .csv file and uploaded to Box [see D3. Methods of Use of Epharmix/CareSignal Intervention Builder].

Hard copies of consent forms and demographic surveys will be kept in a research binder in a locked cabinet in a locked office at the ECRC by the research coordinator until digitally archived. All patient identifiers will be destroyed at the earliest time possible.

### **F3. Data Quality Assurance**

An interim patient chart assessment and analysis of intervention responses will be performed four months after enrollment of the 85th participant. The principal investigator is responsible for monitoring participant responses.

### **F4. Data Analysis, Sample Size Estimation, and Study Power**

As detailed in Section A.2 Pilot Data, we calculated that we need to recruit at least 333 participants to have a power of 90% for a two-sided  $\alpha = 0.05$ , to detect a 10% improvement of the primary outcome. As a Phase II study, we are attempting to identify the effect size of the intervention.

We obtained the estimated improvement in the primary outcome from our pilot study. The number of eligible patients in the ED over a 6-month period were approximately 21% of admitted patients. We needed a sample size of 266 patients, and anticipated that roughly 20% of participants would be lost to follow-up, which means we needed to recruit 333 participants. We calculated our sample size using the G\*Power3 program.

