#### **E2. Data Analysis, Sample Size Estimation, and Study Power**

The sample size from the trial was determined to meet criteria to be sufficiently powered at 90% for a two-sided  $\alpha = 0.05$ , for a 10% improvement of the primary outcome. We will conduct an Intention-to-Treat analysis to test the impact of the intervention on participant follow-up attendance and ED re-admissions. We will also conduct descriptive statistics regarding user engagement.

We might experience missing outcome data if a participant set up a follow-up appointment with a provider who was not their referral provider and is not a part of the BJH EMR network or Missouri Health Connection. These appointments will not be accessible to our study team and a participant may be labeled as *non-compliant* erroneously; however, since most Missouri health clinics participate in the Missouri Health Connection, this issue will be rare and should apply to both the control and intervention arm equally.

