### A2. Epharmix/CareSignal Intervention Builder Summary

An electronic intervention platform was developed by Epharmix/CareSignal, a WUSTL IDEA Labs (ideas.wustl.edu) company, which uses an automated two-way text or phone system for various uses to supplement clinical care, such as tracking patient adherence, collecting additional data, or delivering educational follow-up. The platform is called Epharmix/CareSignal Intervention Builder and is uploaded on Washington University (WU) servers as an application. On this platform our research team has a unique account on which we built a series of messages [see Appendix 5. Pseudocode] to test our hypothesis. Automated text or phone messaging was delivered from this account to intervention participants and participant responses returned directly to this unique account, allowing research team members to supervise responses and have control over the intervention.

Epharmix/CareSignal, Inc. and Epharmix/CareSignal employees are only involved in this project as a service provider, giving WUSTL personnel access to create an account on their platform. One employee, the Chief Developer, assists in aggregating and deidentifying data from our account [see Section D3. Method of Use of Epharmix/CareSignal Intervention Builder].

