#### Exclusion criteria:

1. Unable to be contacted by a phone call and/or SMS text message, or unwilling to provide a phone number.
2. Unwilling to consent and follow the assigned regimen and complete the required follow-up.
3. Non-English speaking.
4. Neurologic, anatomic, or cognitive disorders and thus unable to consent and/or answer text messages/phone calls.
5. Already had a follow-up appointment scheduled before being discharged.

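### The stated 90% power for a 10% improvement does not follow from 266 evaluable (333 recruited): at the attendance rates the documents give, power for a 10-point gain is about 37–65% with 266 and 45–75% with 333.

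*Combined protocol and SAP*

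**What the plan says.** The sample-size claim appears in three places. F4 says "we calculated that we need to recruit at least 333 participants to have a power of 90% for a two-sided" alpha of 0.05 to detect a 10% improvement. E2 repeats 90% power "for a 10% improvement of the primary outcome". The A1 design table lists power of 90% and a total N of about 330.

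F4 gives the derivation: "We needed a sample size of 266 patients, and anticipated that roughly 20% of participants would be lost to follow-up", hence 333 to recruit. Allocation is 1:1 (B6), so 266 is 133 per arm and 333 is 166.5 per arm.

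For the assumed effect, F4 says "We obtained the estimated improvement in the primary outcome from our pilot study" and introduces the calculation with "As detailed in Section A.2 Pilot Data". In the body, however, the section with that number is "A2. Epharmix/CareSignal Intervention Builder Summary", which describes the messaging platform. No control attendance rate, test or scale (absolute or relative) is given for the calculation.

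The only attendance rates in the documents are in B1: 9% to 37.5% historically at this emergency department, and 26% to 56% in general. The primary outcome is binary in F1 (compliant or not) and time to attendance within 120 days in C2.

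**The concern.** A 10-point difference between two proportions normally needs several hundred participants per arm for 90% power, unless the rates are close to 0 or 1. A total of 266 looks too small for the rates in B1.

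What is at stake is how a non-significant result is read. The plan tells the reader that a true 10% improvement would be missed one time in ten. If the true figure is closer to one in two, non-significance alone says little about a 10-point gain, and anyone relying on the stated 90% would over-read it.

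**Working it through.** **Inputs.** Two-sided alpha 0.05 (z = 1.960), power 90% (z = 1.2816), 266 evaluable, 333 recruited and 20% loss, all from F4; 1:1 allocation from B6; control attendance p from 9% to 56%, from B1. The 10% is read first as 10 percentage points, the reading kinder to the plan.

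**The plan's own inflation step.** 266/(1 − 0.20) = 332.5, rounded up to 333. This reproduces.

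**The 266.** For two proportions p and q = p + 0.10, with mean m = (p + q)/2:

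- n per arm = [1.960·√(2m(1−m)) + 1.2816·√(p(1−p) + q(1−q))]² / 0.10²
- power = Φ{[0.10·√n − 1.960·√(2m(1−m))] / √(p(1−p) + q(1−q))}

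At the most favourable documented rate, 9% against 19%, the two square roots are 0.4907 and 0.4856.

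- n = (0.9618 + 0.6223)²/0.01 = 250.9, so 251 per arm and 502 in total.
- Power with 133 per arm = Φ[(1.1533 − 0.9618)/0.4856] = Φ(0.394) = 65.3%.

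At 37.5% against 47.5%, power with 133 per arm = Φ[(1.1533 − 1.3702)/0.6955] = Φ(−0.312) = 37.8%.

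| Control attendance | Power, 266 | Power, 333 | Evaluable N for 90% |
|---|---|---|---|
| 9% | 65.3% | 75.1% | 502 |
| 20% | 46.9% | 55.9% | 784 |
| 26% | 42.2% | 50.5% | 896 |
| 37.5% | 37.8% | 45.4% | 1,024 |
| 45% (lowest power) | 37.0% | 44.6% | 1,048 |
| 56% | 38.6% | 46.4% | 996 |

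The 333 column matters because E2 says "We will conduct an Intention-to-Treat analysis to test the impact of the intervention on participant follow-up attendance and ED re-admissions" and accepts that a visit the team cannot see may be counted as non-compliance, so nearly everyone recruited may be analysed.

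**Does another reading rescue it?**

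- *Exact calculation.* Full enumeration of the uncorrected chi-square test gives 39–66% with 133 per arm and 44–75% with 166 and 167.
- *Time to attendance (C2).* Schoenfeld's formula with exponential times uses HR = ln(1−p−0.1)/ln(1−p) and events = N/2 × (2p + 0.1). At 9%, HR = 2.234 and 266 participants yield 37.2 events, so power = Φ(ln 2.234·√(37.24/4) − 1.960) = 68.9%. Over 9–56% the range is 38.5–68.9% with 266 and 46.2–78.4% with 333.
- *10% as a relative gain.* Comparing p with 1.1p gives 5.7–15.3% with 266 and 5.9–17.9% with 333.
- *Control rate outside the documented range.* For 90% with 266, the formula needs a control rate of 1.9% or lower, or 88.1% or higher; exact enumeration gives 2.6% or 87.4%.

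**What the design can detect.** Over 9–56%, the gain detectable with 90% power is 14.6–19.7 points with 266 and 12.7–17.7 points with 333.

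**Where 266 might have come from.** Two inputs reproduce it, and the documents do not say whether either was used. For 10% against 20%, the formula gives 265.9, that is 266 *per arm* (532 in total). For 10% against 25%, it gives 132.8 per arm, that is 266 in total, with power 90.1%. The first would be a per-arm figure used as a total; the second would mean that the 10% is misstated.

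**Precision.** If 133 per arm show no difference, the 95% half-width is 1.96·√(2p(1−p)/133): 6.9 points at 9% attendance, 9.6 at 20% and 11.6 at 37.5%.

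**The case against.** The strongest objection is that the calculation rests on a pilot rate that the documents do not show. The B1 ranges are background, not a stated design assumption, and the trial population differs: patients are excluded if they "Already had a follow-up appointment scheduled before being discharged", and attendance is counted over 120 days. That stands as a limit on the exact power figures. It does not reverse the direction, because the control rate would have to be about 2–3% or lower, or 87–88% or higher.

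A second objection is that F4 calls this a Phase II study meant to identify the effect size, so power is secondary, and a confidence interval does not depend on planned power. That is a fair reason to report and read the interval. It does not make the 90% correct: the same paragraph claims it, and E2 plans a test of impact.

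A third is that the headline ranges are for the binary outcome, while C2 names time to attendance. This is true, but the log-rank figures differ by only a few points. They also need a translation of the 10% into a difference at 120 days, which the plan does not make.

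**Conclusion.** The concern holds. The 90% power, the 10% improvement and the total of 266 (or 333) cannot all be right at any attendance rate in the documents. The evaluable number needed for a 10-point gain is 1.9 to 3.9 times 266 (502/266 to 1,048/266). The chance of missing such a gain is about 35–63% with 266 analysed and 25–55% with 333, against the 10% that the plan implies.

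This assumes control attendance between 9% and 56%, 1:1 allocation and, for the log-rank figures only, exponential times. The documents do not show which of the three figures is wrong. The error lies in the stated power; it does not bias the estimate or invalidate the test. A 95% interval lying wholly below +10 points would still count against a 10-point gain.

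**What to change.** Add a dated clarification to F4, E2 and the A1 table that keeps the present 90%, 10% and 266 visible. It should:

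1. State the pilot control attendance, the test used, and whether the 10% is absolute or relative.
2. Say whether 266 was a per-arm or a total figure, and correct whichever of the three figures was misstated.
3. State what the design delivers, for example:

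> With 266 analysed (1:1, two-sided alpha 0.05, two proportions) and control attendance of 9–56%, the study has 90% power for an absolute gain of about 15–20 points and 37–65% power for 10 points; with all 333 analysed, about 13–18 points and 45–75%. A non-significant result will be read through its 95% confidence interval.

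4. If the test is a log-rank test, give the corresponding figures (about 38–69% with 266 and 46–78% with 333 for 10 points). If the pilot rate lies outside 9–56%, add the power at that rate.
5. Point the F4 cross-reference to where the pilot data are reported.

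The cost is a change of wording: no extra patients and no change to the analysis. The downside is a less favourable stated power.

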## B. Background & Rationale

### **B1. Background: Adherence to Follow-up Visits After Emergency Department Discharge**

Patient adherence to ED follow-up instructions and appointments varies from 26-56% [1]. According to Kangovi et al. (2012), the most common reason a patient gave for readmission to the ED was “feeling unprepared for discharge” after the first visit [2]. The transition from ED to discharge requires the patient to be responsible for following discharge instructions, obtaining prescriptions, and finding time and resources to attend follow-up visits. Readmissions to the ED are not primarily a result of lack of access to services [3], pointing attention toward follow-up communication, which can improve transition to outpatient care [4-6]. ED clinical staff try to sit down with patients after ED visits to review instructions and sometimes schedule follow-up appointments [7]. An outpatient hemodialysis clinic that tried this model found it to be successful initially, but could not afford the extra staff to sustain it.[8]

Time and money could be saved by implementing automated appointment reminders through voice or text messages. No-show patients were reduced by 10% when one primary care clinic began using a text and phone call reminder for appointments, resulting in a positive cost-benefit analysis [9]. A similar improvement in successful follow-up appointments was found in an ED setting with a diverse population [10]. Historically, successful follow-up appointment rates of patients discharged from the Barnes Jewish Hospital Emergency Department (BJH-ED) have ranged from 9% to 37.5%, the highest rate of follow-ups were for next-day appointments [11]. It’s difficult to know how much of a difference a simple appointment reminder system would make since a previous study of BJH-ED patients found the major identifiable causes for missing appointments were “other” (34%), no transportation (25%), fear of medical cost (18%), feeling better (13%), and unsure of where to go for the visit (9%) [12]. A sophisticated and robust reminder system may be capable of addressing some of these barriers.. Recently complex modalities of electronic follow-up, such as video conferencing or remote physiological monitoring [13-15] have been introduced, further complicating follow-up care adherence, especially in an ED setting.

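### The 20% loss allowance behind N=333 does not fit a chart-read, intention-to-treat outcome, and 333 in total does not give 90% power for a 10-point difference however losses are handled

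*Combined protocol and SAP*

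**What the plan says.** F4 gives 333 as the number to recruit "to have a power of 90% for a two-sided" alpha of 0.05, and "to detect a 10% improvement of the primary outcome". It does not say whether the 10% is absolute or relative. On its source it says "We obtained the estimated improvement in the primary outcome from our pilot study"; no control-arm rate for the calculation appears in the text available. The target is built from 266 patients: the plan "anticipated that roughly 20% of participants would be lost to follow-up, which means we needed to recruit 333 participants".

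Elsewhere the documents describe how the outcome is obtained and analysed:

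- Section E (Follow-up Visit Schedule) requires no study visits, and B6 has attendance identified by review of the electronic record.
- F1 gives the primary outcome two values, compliant or non-compliant. C2 in the first part of the document instead defines it as time to a follow-up visit within 120 days.
- E2 plans an intention-to-treat analysis. On visits to a non-referral provider outside both record networks it says: "These appointments will not be accessible to our study team and a participant may be labeled as" non-compliant in error. It expects that "this issue will be rare" and equal in the two arms.
- B9 keeps data up to withdrawal, and G3 keeps data up to the date on which the investigator stops the intervention.

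No section defines loss to follow-up or says how lost patients enter the primary analysis.

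**The concern.** Dividing by 0.8 is right when 20% of patients supply no outcome, are left out, and the remaining 80% show the full effect. With passive chart review there is no return visit to miss. A patient with no visit on record would ordinarily stay in the denominator, either correctly as a non-attender or wrongly as one whose visit was not visible. Errors of the second kind shrink both arms' rates, and so the difference, instead of reducing the number analysed.

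Two things are at stake. The reader cannot tell whether the intention-to-treat denominator is meant to be 333 or about 266, which leaves room to decide on exclusions after the data are seen. And a stated power of 90% affects how a null result is read, so it should follow from the stated inputs.

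**Working it through.** **Inputs.** From F4: two-sided alpha 0.05, power 90%, improvement 10%, base 266, loss 20%. From B6: 1:1 allocation. *Assumptions:* the 10% is read as 10 percentage points, and the control rate is taken as 10%, 26% or 37.5%. B1 says that rates at this site "have ranged from 9% to 37.5" per cent and cites 26% to 56% from the literature.

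**Step 1: the plan's own figure.** 266/(1 − 0.20) = 332.5, rounded up to 333. It reproduces.

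**Step 2: the base of 266.** Pooled two-proportion formula, with p̄ = (p1 + p2)/2:

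n per arm = [1.960·√(2p̄(1 − p̄)) + 1.282·√(p1(1 − p1) + p2(1 − p2))]² / (p2 − p1)²

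For 10% vs 20%: (0.9897 + 0.6408)²/0.01 = 265.9, so 266 **per arm**, or 532 in total. Totals at other control rates are 502 (9%), 896 (26%), 1,024 (37.5%) and 996 (56%). A total of 266 would need a control rate near 1.9%.

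**Step 3: what scoring as failure does.** If a fraction m of each arm is scored non-compliant regardless of attendance, each rate p becomes (1 − m)p. The required inflation is then approximately (1 − (1 − m)p̄)/((1 − m)(1 − p̄)), which exceeds 1/(1 − m) for any p̄ > 0. With m = 0.20 and the full formula:

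| Control vs intervention | n per arm, full effect | n per arm, diluted | Ratio (plan uses 1.25) |
|---|---|---|---|
| 10% vs 20% | 266 | 345 | 1.30 |
| 26% vs 36% | 447 | 610 | 1.36 |
| 37.5% vs 47.5% | 511 | 735 | 1.44 |

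**Step 4: power at 333 in total for a 10-point difference.** Power = Φ{[(p2 − p1)√n − 1.960·√(2p̄(1 − p̄))] / √(p1(1 − p1) + p2(1 − p2))}.

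| Handling of the 20% | n per arm | 10% | 26% | 37.5% |
|---|---|---|---|---|
| Nobody lost, all counted | 166.5 | 73% | 51% | 45% |
| Excluded, as F4 assumes | 133 | 63% | 42% | 38% |
| Counted and scored as failures | 166.5, rates × 0.8 | 61% | 39% | 34% |

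Example, 10% vs 20% with all counted: (0.1·√166.5 − 0.9897)/0.5 = 0.601, and Φ(0.601) = 0.726.

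**Step 5: the loss model on its own.** Take 266 as correct by choosing, at each control rate, the difference that gives 133 per arm 90% power: 14.6 points at 9%, 18.9 at 26%, 19.7 at 37.5%. Then 333 with nobody lost gives 95% throughout. With 20% scored as failures it gives 89%, 87% and 85%, and 90% would need 348, 372 and 396 in total.

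**Step 6: the time-to-event definition in C2.** The Schoenfeld formula with the same 10-point difference at 120 days needs about 471 (9%), 877 (26%) and 995 (37.5%) in total. Changing the endpoint does not rescue 266.

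**The case against.** The strongest reply is that the plan contains no rule of the kind that would conflict with F4. This stands. A reader might infer that F4 contradicts a scoring rule in E2. But E2 is a caveat about possible mislabelling of one narrow group, those seen outside both record networks; it does not say how everyone without a recorded visit is classified. Nor does calling that group rare contradict 20%, because the 20% is undefined and may describe other patients. B9 and G3 let data stop early, and under C2 such patients could be censored, so it cannot be said that the plan keeps every patient fully observed. What these sections do not do is remove a fifth of patients or give a reason to expect that.

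A reader might also infer that 333 is a miscalculation. As division it is correct, and if nobody is lost the extra patients only raise power.

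Thirdly, low power should not be blamed on the loss model. This stands too: against the plan's own 133 per arm, scoring as failures instead of excluding costs only about 1.5 to 4 points (63% to 61%, 42% to 39%, 38% to 34%).

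Finally, if the pilot rates were themselves read from charts, unseen visits are already in them and the row with all counted is the relevant one. The documents do not say.

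**Conclusion.** The point holds in two parts of unequal weight. The 20% allowance does not match the way the outcome is ascertained and analysed, and the plan leaves the handling of lost patients undefined. By itself this matters modestly: 95% power if nobody is lost, about 85% to 89% if 20% are scored as failures, both conditional on 266 being right.

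The more important part is that 90% at 333 in total is not delivered for a 10-point difference under any of the three loss treatments. The best case among the attendance rates in the documents is 75%, at a 9% control rate with all patients counted. Most of the shortfall comes from the base of 266. That 266 is the per-arm number for 10% vs 20% invites the inference that a per-arm figure was used as a total; the documents do not show the inputs, so this remains a coincidence to be checked.

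All power figures rest on assumed control rates and an absolute 10-point effect. A relative 10% would make matters far worse: about 7,132 patients in total at a 37.5% control rate.

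**What to change.** In F4 and E2:

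1. State the control rate, whether the 10% is absolute or relative, and the test used in G\*Power.
2. State that all randomised patients are in the primary analysis, and how withdrawn patients (B9), patients stopped by the investigator (G3) and patients with unseen visits are scored or censored, consistently with whichever primary outcome definition (F1 or C2) is kept.
3. Replace the 90% with the power at N=333 with all patients counted, for missed-visit fractions of 0 and 0.20, with both arms' rates multiplied by one minus that fraction. Use design assumptions, not observed results.
4. Say whether the 20% in F4 and the rare cases in E2 are the same group; if so, use one figure.

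The cost is a rewritten sample size paragraph and a few sentences on outcome handling. No patients or procedures are added. The stated power becomes less favourable.
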